### 9.2. Adverse Events

Adverse events are coded using the Medical Dictionary for Regulatory Activities (MedDRA) Version 13.0 and displayed in tables and listings using System/Organ/Class (SOC) and Preferred Term.

Summaries of adverse events will be generated for those events that are considered treatment emergent, where treatment emergent is defined as any adverse event that emerges during treatment in study RP103-04, having been absent pretreatment, or worsens relative to the pretreatment state. All adverse event summaries will be presented for each subpopulation and overall.

An overview summary table of AEs will be presented including the number and percentage of subjects reporting a treatment-emergent AE for the following categories:

- Subjects reporting at least one AE
- Subjects reporting at least one treatment-related AE
- Subjects reporting at least one serious AE (SAE)

---

- Subjects reporting at least one Grade  $\geq 3$  AE
- Subjects reporting at least one AE leading to discontinuation of study

The number and percentage of subjects who experienced at least one AE will be summarized overall and for each SOC and each PT. The percentage will be based on the number of subjects in the Safety Population. Each subject will contribute at most one count per summarization category. In other words, if a subject has more than one AE with same PT, the subject will be counted only once for that PT. Similarly, if a subject has more than one AE for a SOC, the subject will be counted only once in that SOC and PT. SOCs (and PTs within each SOC) will be sorted in summary tables by descending frequency of each.

Similarly, the number and percentage of subjects with any treatment-emergent SAEs, with any treatment-emergent adverse events assessed by the Investigator as related to treatment, and with any treatment-emergent adverse events leading to discontinuation of study and with any SAE will be summarized by SOC and PT.

The number and percentage of subjects with any treatment-emergent adverse events will be summarized by relationship to study drug (not related, unlikely related, possibly related, probably related, definitely related, unknown) and severity (mild, moderate, severe, life-threatening, death, unknown) by SOC and PT. In these tabulations, each subject will contribute only once (i.e., the most related occurrence or the most intense occurrence) to each of the incidence rates in the descriptive analysis, regardless of the number of episodes – e.g. worst grade, per subject, per toxicity.

In addition, summaries of the incidence of subjects with AEs, and SAEs, by study year of onset (Year 1, Year 2 and Year 3 or later) will be generated. Treatment-emergent gastro-intestinal adverse events, i.e. adverse events with SOC of “gastrointestinal disorders”, will also be summarized by frequency of episodes (1-3 occurrences vs 4 or more) by PT. Similarly, treatment-emergent treatment-related gastro-intestinal adverse events will be summarized.

All adverse events occurring on study will be listed in subject data listings.

By-subject listings also will be provided for the following: serious adverse events, adverse events for laboratory abnormalities, and adverse events leading to study discontinuation.

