**Individual patient dosing will be stopped if:**

- A patient exhibits a treatment-emergent adverse event of Common Terminology Criteria for Adverse Events (CTCAE) grade 3 or higher and not likely related to the underlying disease.

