**A patient will be discontinued if they exhibit an:**

- Unexplained fever ( $> 38.5^{\circ}\text{C}$ ) for  $> 24$  hours.

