### **11. Statistical Plan**

#### **11.1. Statistical Methods**

This Study is designed to assess the safety and tolerability of Cysteamine Bitartrate Delayed-release Capsules (RP103) in patients with cystinosis.

A statistical analysis plan will be developed that describes in detail, the statistical methods to be used and will be finalized prior to database lock. This document may modify the plans outlined in the protocol; however, any major modifications of the Study endpoint definitions will be reflected in a protocol amendment.

Demographic and disposition data, drug administration, medical history, prior and concomitant medications, AEs, clinical laboratory measurements, vital signs, ECG measurements and physical examination findings will be summarized. Descriptive summaries of mean and mean changes from screening will be presented for the safety laboratory parameters (hematology, serum chemistry and urinalysis, as applicable),

vital signs and ECGs. The overall incidence of subjects with adverse events will be summarized by System Organ Class (SOC) and Preferred Term (PT) using the latest version of the Medical Dictionary for Regulatory Activities (MedDRA) coding dictionary. Summaries by maximum severity, drug –relationship (as determined by the investigator) and drug discontinuation will also be presented. In addition, summaries of annualized exposure adjusted AE rates as well as summaries of the incidence of subjects with AEs by study year of onset (Year 1, Year 2 and Year 3 or later) will be generated. The overall incidence of subjects with serious adverse events (SAEs) will be summarized by SOC and PT. The annualized exposure adjusted SAE rates as well as the incidence by study year will also be tabulated. Safety laboratory values outside reference ranges will be flagged in laboratory listings.

AEs will be categorized using MedDRA, and listed by verbatim, primary term and SOC. SAEs will include MedDRA coding of primary and secondary (non serious) event terms.

[REDACTED]

[REDACTED]

[REDACTED]

[REDACTED]

Cysteamine concentrations and WBC cystine levels will be summarized per patient.

*Pharmacokinetics:*

The steady-state plasma concentration profiles of cysteamine will be determined for each patient and the  $AUC_{0-t}$ ,  $C_{min}$ ,  $C_{max}$ ,  $T_{max}$  and  $t_{1/2}$  PK parameters will be estimated using non-compartmental methods.

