### 9.1. Study Drug Exposure

Duration of study drug exposure will be calculated as the duration from the date of first dose of RP103 in Study RP103-04 to the date of last dose as:

Exposure (days) = (Last Dose Date – First Dose Date + 1) – number of days dosed with Cystagon

Duration of exposure will be summarized for each subpopulation and overall using descriptive statistics. The number and percentage of subjects with duration of exposure in each category ( $\leq$  12 months,  $>$  12 months and  $\leq$  24 months,  $>$  24 months and  $\leq$  36 months,  $>$  36 months and  $\leq$  48 months,  $>$  48 months and  $\leq$  60 months, and  $>$  60 months) will also be summarized.

The mean RP103 dose (mg/m^2/day) will be summarized over time using collected visits.

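### The protocol commits to summarising adverse events by discontinuation of drug; SAP 9.2 tabulates and lists only those leading to discontinuation of the study, and the readable text does not declare the change

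*SAP*

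**What the plan says.** **Protocol.** Section 11.1 lists the AE summaries: by SOC and preferred term, by maximum severity, by relationship to drug, and by discontinuation. On the last item it says "and drug discontinuation will also be presented". The statistical part of the synopsis makes the same commitment. The primary objective (Section 5.1.1) covers both safety and tolerability of long-term dosing.

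**SAP.** Section 9.2 uses leaving the study as the criterion in all three places:
- Overview table: "Subjects reporting at least one AE leading to discontinuation of study".
- SOC/PT table: subjects "with any treatment-emergent adverse events leading to discontinuation of study and with any SAE will be summarized by SOC and PT".
- By-subject listings: "adverse events for laboratory abnormalities, and adverse events leading to study discontinuation".

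No readable text in the SAP plans a display of AEs by what was done with RP103.

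**Declared changes.** SAP Section 10 lists departures from Amendment 9 of the protocol. Two of its three bullets can be read. One moves gastric acid reducing medication from an exploratory to a safety endpoint, and the other drops the exposure-adjusted AE rates. Neither mentions discontinuation. The third bullet is redacted.

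**The concern.** Stopping a drug and leaving a study are different events, and a long-term tolerability study is mainly interested in the first. If a patient can come off RP103 because of an AE and remain under follow-up, the protocol's category counts that patient and the SAP's does not.

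None of the other AE displays supplies the missing information. The overall, related, serious, Grade 3 or higher and severity tables would contain the event but would not show that it stopped the drug. The serious AE table cannot stand in for it, because Protocol 10.1 states that stopping study drug does not by itself make an event serious. The mean-dose summary in SAP 9.1 is not linked to AEs. At stake is one specific tolerability figure, which the protocol named and the SAP does not produce.

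**Working it through.** The documents give no count, rate or target for this point, so there is no plan figure to reproduce. The check sets the passages side by side and asks which patients the two criteria classify differently.

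**Step 1. Do the documents allow time off RP103 without a study exit?**
- SAP 9.1 defines exposure as last dose date minus first dose date plus 1, less the "number of days dosed with Cystagon". The first dose is the first RP103 dose in this study. The formula itself does not say which drug the last dose refers to. If it is RP103, the subtraction matters only for patients who took Cystagon between two periods on RP103. If it can be either drug, the subtraction also covers Cystagon days at the end, which might simply belong to patients leaving the study. On the first reading the SAP expects time off RP103 within the study; on the second it allows for it.
- Protocol 10.1.1 has one heading beginning "Individual patient dosing will be stopped if", triggered by certain treatment-emergent events of CTCAE Grade 3 or higher. A separate heading reads "A patient will be discontinued if they exhibit an". The first does not say that the patient then leaves the study. The second does not say whether drug or study is meant.
- The causality definitions in Protocol 10.2 refer to rechallenge, which presupposes stopping and restarting the drug.

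So the plan provides for time off RP103 without stating that it ends participation.

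**Step 2. How does each criterion classify the possible cases?**
1. An AE stops RP103 permanently and the patient leaves the study: counted under both.
2. An AE stops RP103 and the patient stays in the study: counted under the protocol's criterion, not under the SAP's.
3. An AE interrupts RP103, which is later resumed: not counted under the SAP, and not clearly promised by the protocol, which names discontinuation and not interruption.
4. An AE leads to a lower dose and the patient stays: counted under neither.

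The departure from the protocol is case 2. Cases 3 and 4 are outside the commitment.

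**Step 3. How many patients are in case 2?** The documents do not say. Three protocol sections point to a small number:
- Section 11.6 has dosing continue until the patient withdraws or is withdrawn.
- Section 7.3 times the visit after premature study discontinuation from the last dose of study drug.
- Section 9.1.6 describes the move back to Cystagon for patients who have terminated from the study.

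**Step 4. Is the change declared?** Not in the readable bullets of SAP Section 10. The redacted bullet and the redacted table list in SAP Section 12 could contain an entry, so its absence is established only for the readable text.

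**The case against.** The strongest reply is that the two labels count nearly the same people. The protocol describes no off-drug follow-up status. Where a patient does not tolerate the dose, Section 8.5 and the visit sections give two outcomes: dose adjustment or termination from the study. On that reading a permanent stop is normally an exit, and the SAP wording may only be loose. Protocol 11.1 also allows the SAP to modify the protocol's analysis plans.

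Much of this stands, and it limits the size of the point. It does not remove it. Section 10.1.1 states a dosing stop without stating an exit, and the permission to modify does not explain why this change goes unmentioned when another dropped AE analysis is declared. If the two events always coincide, restoring the protocol's category costs nothing.

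A reader might infer several stronger claims that the documents do not support:
- *That these events vanish from the tolerability results.* They remain in the other AE tables and in the full AE listing. Events that trigger the Section 10.1.1 dosing stop also fall in the Grade 3 or higher row. Only the link to stopping drug is lost.
- *That the Cystagon days are tolerability failures.* SAP 9.1 gives no reason for those days, and nothing ties them to AEs.
- *That the protocol promised tables of interruptions or dose reductions.* It promised drug discontinuation only.
- *That the understatement can be quantified.* At the enrolment ceiling of 60, one patient weighs 1/60 = 1.7 percentage points. That is the weight of a single patient, not an estimate of how far the figure would move.

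**Conclusion.** The mismatch holds. The protocol commits to AE summaries by drug discontinuation, the SAP substitutes study discontinuation in every display it describes, and the readable text does not declare the substitution. Any patient whose AE stopped RP103 while they stayed in the study would be missing from the discontinuation row, the SOC/PT table and the listing.

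The size cannot be derived and may be small. The conclusion rests on two conditions: that the redacted parts of SAP Sections 10 and 12 contain no such declaration or table, and that at least some AE-related drug stops occur without study exit, which the documents allow but do not show to have happened. The point is worth correcting because it bears on tolerability, which is part of the primary objective. It does not undermine the rest of the AE analysis.

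**What to change.** 1. In the SAP 9.2 overview table, SOC/PT table and by-subject listing, add AEs leading to discontinuation of RP103, as the protocol states. Keep study discontinuation as a separate row, so that any difference between the two is visible.
2. Optionally, and beyond what the protocol promises, add a row for AEs leading to RP103 interruption, switch to Cystagon or dose reduction, where the action taken was recorded. Protocol 6.1.2 has the investigator's visit reviews documented with actions and reasons, and Section 10.3 requires action taken in SAE reports. The documents do not say that every AE record carries such a field, so this needs checking first.
3. If the drug-discontinuation summary is dropped on purpose, state and justify that in SAP Section 10. If the sponsor holds that the two events always coincide in this study, that can be the justification.

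The cost is a few extra rows and one more table, plus the work of confirming that AE-related drug stops can be identified from the recorded data. Tolerability figures may look slightly less favourable.

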### **6.3. Duration**

Patients will be followed until Study termination; which can occur by patient, physician or Sponsor request, or until the RP103 drug is available through the appropriate marketing approval, or until the Sponsor terminates development of RP103 for this indication for any reason. Approximate treatment time in the Study is 96 months. However, a subject may withdraw consent or be withdrawn from the study prior to completion.

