### **3. SUBJECT POPULATIONS**

#### **3.1. Population Definitions**

Two populations for this study are planned for analysis as described below.

**Safety Population:** The Safety Population consists of all subjects who received at least one dose of study drug (RP103).

**PK/PD Population:** All subjects who have at least one PK/PD measurement are included in the PK/PD population.

Each one of these 2 populations is then partitioned in 3 subpopulations:

A: Subjects who completed Study RP103-03

B: Subjects  $\leq$  6 years old

C: Renal Transplant subjects

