#### 4.2.7. Withdrawals, Dropouts, Loss to Follow-up

---

There are no planned exclusions due to withdrawals, dropouts, or loss to follow-up.

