## 9. SAFETY ANALYSES

Safety summaries will be produced for the Safety Population for each subpopulation and overall.

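### AE and SAE incidence by study year of onset has no year-specific number at risk, and its open-ended last bin can span six years beside two one-year bins, so the time pattern can mislead even when risk is constant

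*SAP*

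**What the plan says.** SAP 9.2 plans summaries of subjects with AEs and with SAEs "by study year of onset (Year 1, Year 2 and Year 3 or later) will be generated". No denominator accompanies that sentence. An earlier paragraph of the same section, on overall, SOC and PT incidence, says "The percentage will be based on the number of subjects in the Safety Population". The opening of SAP 9 sets the default: "Safety summaries will be produced for the Safety Population for each subpopulation and overall". SAP 3.1 defines the Safety Population by a single dose of RP103, with no condition on remaining in the study. SAP 4.2.7 adds: "There are no planned exclusions due to withdrawals, dropouts, or loss to follow-up".

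On follow-up, Protocol 6.3 says "Approximate treatment time in the Study is 96 months" (the synopsis says up to 96 months). It also lets follow-up end at a patient's, physician's or sponsor's request, or run only "until the RP103 drug is available through the appropriate marketing approval". Patients who did not complete RP103-03 may enter only after that study has been analysed (Protocol 6.1). SAP 9.1 plans exposure categories from 12 months or less to more than 60 months.

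Protocol 11.1 paired the by-year table with annualised, exposure-adjusted AE and SAE rates. SAP 10 drops the exposure-adjusted AE analysis, and SAP 9.2 lists no such rate for SAEs.

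**The concern.** The primary objective is long-term safety and tolerability. In the readable SAP text, the by-year table is the only AE summary arranged by time, so it is where a reader would look to see whether events become more or less frequent with continued treatment.

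Two features distort that comparison. First, a subject who left in Year 1, or who entered too late to reach Year 3, cannot have a Year 3 event under observation. If everyone ever dosed forms the denominator, that subject counts as event-free in Year 3. Second, the last bin can be six times as long as each of the others, so more subjects have at least one event in it simply because there is more time. The two errors push in opposite directions and neither can be seen from the percentages.

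Because AE summaries are also split by subpopulation, later entrants with less possible follow-up could show a lower Year 3 or later percentage than RP103-03 completers at the same yearly risk.

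**Working it through.** The plan gives no AE rate, withdrawal rate or target figure for this table, so there is nothing to reproduce. What follows is illustration. Every risk and exit rate is an assumption, and the true risk is held constant throughout.

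**Inputs from the documents.** Duration is about 96 months = 8 years (Protocol 6.3), so Year 3 or later covers at most Years 3 to 8, which is 6 years. SAP 9.1 has a category above 60 months, so the SAP itself allows for exposure beyond Year 5. Enrolment is at most 60 (Protocol synopsis).

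**Dilution of a single year.** Reported % = % among those still treated × fraction still treated. If 70% remain, 40% is reported as 0.70 × 40 = 28%. If 50% remain, it is reported as 20%.

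**Whole-population denominator, 10% yearly risk, 15% leaving at the end of each year.**
- Year 1: 10.0%.
- Year 2: 0.85 × 0.10 = 8.5%.
- Year 3 or later: the chance of passing a year with neither event nor exit is 0.90 × 0.85 = 0.765. So 0.85^2 × 0.10 × (1 − 0.765^6)/(1 − 0.765) = 0.7225 × 0.10 × 3.402 = 24.6%.
- With no exits the last column would be 1 − 0.9^6 = 46.9%.

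**Changing only the denominator.** Dividing the last column by those at risk at its start gives 24.6/0.7225 = 34.0%, still far from 10%. With at-risk denominators and single-year columns, every column reads 10.0%.

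**Sensitivity, using a second model.** Assume a constant AE hazard h and a constant exit hazard w, with exits spread through the year. For a window of length L starting at time a, the whole-population percentage is exp(−wa) × h/(h+w) × [1 − exp(−(h+w)L)].

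| AE risk per full year | Exit per year | Year 1 | Year 2 | Year 3 or later |
|---|---|---|---|---|
| 10% | 10% | 9.5% | 8.5% | 29.1% |
| 10% | 40% | 7.9% | 4.7% | 6.0% |
| 30% | 10% | 28.6% | 25.7% | 58.6% |
| 30% | 20% | 27.1% | 21.7% | 38.2% |
| 30% | 30% | 25.5% | 17.8% | 24.2% |
| 60% | 30% | 51.8% | 36.3% | 35.3% |

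Year 2 falls below Year 1 in every row, by exactly the fraction gone by the end of Year 1. The last column lies above Year 1 in three rows and below it in three. In the 30%/20% row, at-risk denominators with the pooled bin kept give 27.1%, 27.1% and 59.6%. With single years, Years 1, 2 and 3 are all 27.1%. That figure is below 30% because some subjects leave part-way through a year, which is why person-years are worth showing too.

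**The case against.** The strongest point is that the by-year denominator is inferred. The quoted percentage rule sits in the overall, SOC and PT paragraph, while the by-year sentence comes later with no rule of its own. The list of planned tables in SAP 12 is redacted and could show a year-specific N. A reader might conclude that the SAP prescribes the whole Safety Population for this table. It does not say so; that is only the natural reading of the section default and the one stated rule. Nor does SAP 4.2.7 settle it: planning no exclusions for withdrawal means data are kept, and says nothing about who is at risk in a given year.

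Several mitigations also stand in part. The exposure bands in SAP 9.1 let a careful reader approximate how many subjects passed 12 and 24 months. Summaries by subpopulation separate RP103-03 completers from the young children and transplant recipients who came from outside that study. AEs are listed by subject. The last bin is openly labelled as open-ended and is the same in the protocol. Six years is an upper limit, and the table is descriptive.

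None of this puts a number at risk beside the by-year percentages. Exposure is tabulated separately and excludes days on Cystagon, so it only approximates time since first dose. The length of the last bin is written in the SAP and needs no inference.

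**Conclusion.** The point holds as a defect of specification and of binning. The readable SAP defines no number at risk per study year, the only stated rule points to everyone ever dosed, and the last bin is open-ended. No other planned AE summary in the readable text allows for unequal follow-up.

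The size for this trial is unknown, because the documents give neither its withdrawal pattern nor its AE rates. In the main illustration a constant 10% yearly risk appears as 10.0%, 8.5% and 24.6%; that rests on the assumed 15% yearly exit and a full six-year last bin.

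A reader might infer that the table will always show improving tolerability followed by late toxicity, or that all later figures are diluted. Neither is supported. Year 2 is diluted whenever subjects have left by then. In the last column, pooling and dilution oppose each other: at a 30% yearly risk it falls below Year 1 once yearly exit reaches about 30%, and at a 60% risk once it reaches about 20%. What can be said is that the pattern may be false in either direction.

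**What to change.** In SAP 9.2, state that each year-of-onset column uses as denominator the subjects still receiving RP103 at the start of that study year. Print that N, and preferably the person-years, in the column header. Replace Year 3 or later with single-year columns, or with the 12-month bands of SAP 9.1.

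If a final open-ended band is kept, report it per person-year. Person-time should run to the subject's first event in the band or to exit. In the main illustration that is 0.7225 × 3.402 = 2.46 subject-years per enrolled subject, and 0.246/2.46 recovers the 10% yearly risk. Both parts are needed, because the denominator change alone leaves the pooled column at 34.0%.

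The cost is SAP wording and header counts from dose dates already needed for the exposure table; no new data are required. Late columns will be small. With 60 subjects and the assumed 15% exit, about 60 × 0.85^2 = 43 start Year 3 and 60 × 0.85^7 = 19 start Year 8, before any split by subpopulation. Year 2 percentages rise (8.5% to 10.0% in the illustration). The pooled late figure gives way to single-year figures that are typically lower (24.6% to 10.0% in each year), so the change does not simply make the later years look worse.
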